### **4.5.5 Tumor and Response Evaluations**

All evaluable or measurable disease must be documented at screening and re-assessed at each subsequent tumor evaluation. Response will be assessed by the IRC and the investigator on the basis of PET and CT scans using the Lugano 2014 criteria (see [Appendix 5](#)). In this study, the Lugano 2014 criteria for a PET-CT• based CR have been

slightly modified to require normal bone marrow for patients with bone marrow involvement at screening (see [Appendix 5](#)). Additionally, designation of PET-CT • based PR requires that CT-based response criteria for a CR or PR be met in addition to the PET-CT • based response criteria for a PR (see [Appendix 5](#)).

#### **4.5.5.1 Radiographic Assessments**

PET scans should include the base of the skull to mid-thigh. Full body PET scans should be performed when clinically appropriate.

CT scans with oral and IV contrast should include chest, abdomen, and pelvic scans. CT scans of the neck should be included if clinically indicated (i.e., if evidence of disease on physical examination) and must be repeated throughout the study if there is disease involvement at baseline.

PET-CT scans and diagnostic CT scans should be acquired according to a standardized imaging manual, which will be provided to all sites.

If contrast is medically contraindicated (e.g., patients with contrast allergy or impaired renal clearance), MRI scans of the chest, abdomen, and pelvis (and neck, if clinically indicated) and a non-contrast CT scan of the chest may be performed. If MRI scans cannot be obtained, CT scans without contrast are permitted as long as these allow consistent and precise measurement of the targeted lesions during the study treatment period.

The same radiographic assessment modality must be used for all response evaluations to ensure consistency across different timepoints (including unscheduled assessments).

A full tumor assessment, including radiographic assessment, must be performed any time disease progression or relapse is suspected.

Additional details regarding imaging procedures will be provided in the Imaging Manual.

#### **4.5.5.2 Bone Marrow Assessments**

Bone marrow examinations are required at screening for staging purposes in all patients and should be performed within approximately 3 months prior to Day 1 of Cycle 1.

If bone marrow infiltration is present at screening, a bone marrow biopsy is required at the EO1 response assessment for all patients who may have achieved a CR. In patients with a PR and continued bone marrow involvement, a subsequent bone marrow examination may be required to confirm a CR at a later timepoint.

Any additional (unscheduled) bone marrow examinations performed during the study will be at the discretion of the investigator.

## **4.5.6 Laboratory, Biomarker, and Other Biological Samples**

### **4.5.6.1 Local Laboratory Assessments**

Samples for the following laboratory tests will be analyzed at the study site's local laboratory for analysis:

- Hematology: hemoglobin, hematocrit, platelet count, RBC count, WBC count, percent or absolute WBC differential count (neutrophils, eosinophils, basophils, monocytes, lymphocytes, and other cells)
- Serum chemistry: sodium, potassium, glucose, BUN or urea, creatinine, calculated creatinine clearance, calcium, total bilirubin, direct bilirubin, total protein, albumin, ALT, AST, alkaline phosphatase, amylase, lipase, LDH, and uric acid
- $\alpha_2$  microglobulin
- Coagulation: INR, aPTT (or PTT), and PT
- Pregnancy test
  - All women of childbearing potential will have a serum pregnancy test at screening (within 7 days of Day 1 of Cycle 1). Because of the suspected effect of idasanutlin on embryo-fetal development, monthly pregnancy testing is strongly recommended for women of childbearing potential ([CTFG 2014](#))
- Viral serology
  - Hepatitis B testing includes HBsAg and total HBcAb.
  - Hepatitis C testing includes HCV antibody.
- Quantitative immunoglobulins: IgA, IgG, and IgM
- *Bone marrow assessment*

### **4.5.6.2 Central Laboratory Assessments**

The following samples will be sent to one or several Sponsor-designated central laboratories or to the Sponsor for analysis:

- Serum samples for obinutuzumab PK analysis using a validated assay
- *Serum samples for rituximab PK analysis using a validated assay*
- Plasma samples for idasanutlin (and metabolites) PK analysis using a validated assay
- Tumor tissue samples and the corresponding pathology report for retrospective central confirmation of the diagnosis of FL or DLBCL. This tissue sample will also be used for exploratory research on candidate biomarkers (see [Table 13](#))

The specimen must contain adequate evaluable tumor cells ( $\geq 20\%$  for excisional biopsy and  $\geq 50\%$  for core biopsy).

FFPE tissue blocks are preferred over slides. Tissue blocks that are not formalin fixed will be accepted in countries that use a fixative other than paraformaldehyde, but information on the type of fixative should be included. If a tissue block is not available,  $15 \times 20$  serial, freshly cut, unstained slides accompanied by a punch biopsy may be sent. A tumor block or punch biopsy is

required for construction of a tissue microarray. If less than 15•20 unstained serial slides are available, the study site should consult the Sponsor (or delegate) regarding the acceptability of a fewer number of slides.

If the archival tissue is unavailable a pretreatment core needle tumor biopsy is required. Cytological or fine-needle aspiration samples are not acceptable.

If a patient has had anti-lymphoma therapy between the time of the prior biopsy and treatment initiation, a repeat biopsy is highly encouraged.

The sample should be shipped according to instructions provided in the laboratory manual. The remainder of the tissue blocks will be returned to the local pathology laboratory, according to country-specific procedures.

- Whole blood and serum samples will be collected for exploratory research on candidate biomarkers, including but not limited to those listed in [Table 13](#).

**Table 13 Proposed Non-Inherited Biomarkers**

Sample Type	Timing	Proposed Non-Inherited Biomarkers
Archival or fresh tumor tissue	Prior to study (archival) or baseline (fresh) Fresh biopsy at progression	
 
• For DLBCL patients only: DLBCL cell-of-origin subtype (ABC vs. GCB), BCL2, MYC
 
• Lymphoma-related genetic changes (DNA) and gene expression (mRNA)
 
• Identification of lymphoma clone identifier (B-cell receptor sequence) for subsequent MRD assessment in blood
 
• TP53 mutation status
 
• IHC (ex p53, MDM2, CDKN2A, XPC, PUMA, BCL2)
 
• mRNA expression for MDM2, XPC, BBC3(PUMA,) and CDKN2A (p16/INK4A, ARF.)
 

Serum	Baseline and subsequent timepoints during treatment	
 
• MIC-1
 

Whole blood for MRD	Baseline and subsequent timepoints during and after treatment	
 
• Circulating lymphoma cells
 
• Cell-free circulating tumor DNA
 

Whole blood	Baseline and subsequent timepoints during and after treatment	
 
• Lymphocyte immunophenotyping, including B-cell counts (CD19), T-cell counts (CD3, CD4, and CD8), and NK cell counts (CD16 and CD56)
 

ABC = activated B cell-like; DLBCL = diffuse large B-cell lymphoma; GCB = germinal-center B cell-like; IHC = immunohistochemistry; MDM2 = murine double minute 2; MRD = minimal residual disease; NK = natural killer.

Note: Exploratory biomarker research may include but will not be limited to the biomarkers listed in this table.

Samples collected for biomarker analyses may be used for exploratory biomarker research, assay development purposes, and additional safety and immunogenicity assessments, as appropriate.

Based on ongoing analysis of data, the Sponsor may choose to stop any analysis, timepoint or sample type if the data does not support a strong scientific justification to continue.

Biological samples will be destroyed within 5 years after the final clinical study report has been completed. Remaining samples will be stored for exploratory research if the patient provides Roche Clinical Repository (RCR) consent.

#### **4.5.7 Electrocardiograms**

Single, resting, 12-lead ECG recordings will be obtained at specified timepoints, as outlined in the schedule of activities (see [Appendix 1](#) and [Appendix 2](#)), and may be obtained at unscheduled timepoints as clinically indicated. ECGs for each patient should be obtained using the same machine wherever possible. All ECG recordings must be performed using a standard high-quality, high-fidelity digital electrocardiograph machine equipped with computer-based interval measurements. Lead placement should be as consistent as possible. ECG recordings must be performed after the patient has been resting in a supine position for at least 10 minutes. All ECGs are to be obtained prior to other procedures scheduled at that same time (e.g., vital sign measurements, blood draws) and under no conditions while patient is receiving a premedication/study drug IV infusion. Circumstances that may induce changes in heart rate, including environmental distractions (e.g., television, radio, conversation) should be avoided during the pre-ECG resting period and during ECG recording.

For safety monitoring purposes, the investigator or designee must review, sign, and date all ECG tracings. Paper copies of ECG tracings will be kept as part of the patient's permanent study file at the site. The following should be recorded in the appropriate eCRF: ECG abnormality (including waveform); heart rate; PQ, PR, RR, and QRS intervals; and QT interval and corrected QTcF interval based on the machine readings of the individual ECG tracings. Any morphologic waveform changes or other ECG abnormalities must be documented on the eCRF.

If at a particular postdose timepoint the mean QTcF is > 500 ms and/or 60 ms longer than the baseline value, another ECG must be recorded, ideally within the next 5 minutes, and ECG monitoring should continue until QTcF has stabilized on 2 successive ECGs. Standard-of-care treatment may be instituted per the discretion of the investigator. If a PK sample is not scheduled for that timepoint, an unscheduled PK sample should be obtained. The investigator should also evaluate the patient for potential concurrent risk factors (e.g., electrolyte abnormalities, dehydration, co-medications known to prolong the QT interval, severe bradycardia) and provide this information to the eCRF.

ECG sampling assessment windows are as follows:

- Pre-dose: within 2 hours prior to idasanutlin dosing
- Post-dose: 6 hours after idasanutlin dose ( $\pm$  5%; equal to 18 minutes) or after the end of obinutuzumab *or rituximab* infusion, whichever occurs later

#### **4.5.8 Samples for Roche Clinical Repository**

##### **4.5.8.1 Overview of the Roche Clinical Repository**

The RCR is a centrally administered group of facilities used for the long-term storage of human biologic specimens, including body fluids, solid tissues, and derivatives thereof (e.g., DNA, RNA, proteins, and peptides). The collection and analysis of RCR specimens will facilitate the rational design of new pharmaceutical agents and the development of diagnostic tests, which may allow for individualized drug therapy for patients in the future.

Specimens for the RCR will be collected from patients who give specific consent to participate in this optional research. RCR specimens will be used to achieve the following objectives:

- To study the association of biomarkers with efficacy, adverse events, or disease progression
- To increase knowledge and understanding of disease biology
- To study drug response, including drug effects and the processes of drug absorption and disposition
- To develop biomarker or diagnostic assays and establish the performance characteristics of these assays

##### **4.5.8.2 Approval by the Institutional Review Board or Ethics Committee**

Collection and submission of biological samples to the RCR is contingent upon the review and approval of the exploratory research and the RCR portion of the Informed Consent Form by each site's Institutional Review Board or Ethics Committee (IRB/EC) and, if applicable, an appropriate regulatory body. If a site has not been granted approval for RCR sampling, this section of the protocol (Section 4.5.8) will not be applicable at that site.

##### **4.5.8.3 Sample Collection**

The following samples will be collected for research purposes, including but not limited to research on dynamic (non-inherited) biomarkers related to obinutuzumab, *rituximab*, and idasanutlin, FL, DLBCL, or other types of cancer:

- Remaining tumor tissue samples (except for remaining blocks, which will be returned to the sites)
- Blood for serum
- Leftover peripheral blood

For all samples, dates of consent should be recorded on the associated RCR page of the eCRF. For sampling procedures, storage conditions, and shipment instructions, see the laboratory manual.

RCR specimens will be destroyed no later than 15 years after the date of final closure of the associated clinical database. The RCR storage period will be in accordance with the IRB/EC-approved Informed Consent Form and applicable laws (e.g., health authority requirements).

#### **4.5.8.4 Confidentiality**

##### **Confidentiality for All Roche Clinical Repository Specimens**

Specimens and associated data will be labeled with a unique patient identification number.

Patient medical information associated with RCR specimens is confidential and may be disclosed to third parties only as permitted by the Informed Consent Form (or separate authorization for use and disclosure of personal health information) signed by the patient, unless permitted or required by law.

Data generated from RCR specimens must be available for inspection upon request by representatives of national and local health authorities, and Roche monitors, representatives, and collaborators, as appropriate.

Data derived from RCR specimen analysis on individual patients will generally not be provided to study investigators unless a request for research use is granted. The aggregate results of any research conducted using RCR specimens will be available in accordance with the effective Roche policy on study data publication.

Any inventions and resulting patents, improvements, and/or know-how originating from the use of the RCR data will become and remain the exclusive and unburdened property of Roche, except where agreed otherwise.

##### **Additional Confidentiality for Specimens Used for Genetic Research**

Given the sensitive nature of genetic data, Roche has implemented additional processes to ensure patient confidentiality for RCR specimens collected for genetic research. Upon receipt by the RCR, specimens for genetic research are "double-coded" by replacing the patient identification number with a new independent number. Data generated from the use of these specimens and all clinical data transferred from the clinical database and considered relevant are also labeled with this same independent number. A "linking key" between the patient identification number and this new independent number is stored in a secure database system. Access to the linking key is restricted to authorized individuals and is monitored by audit trail. Legitimate operational reasons for accessing the linking key are documented in a standard operating procedure.

Access to the linking key for any other reason requires written approval from the Pharma Repository Governance Committee and Roche's Legal Department, as applicable.

#### **4.5.8.5 Consent to Participate in the Roche Clinical Repository**

The Informed Consent Form will contain a separate section that addresses participation in the RCR. The investigator or authorized designee will explain to each patient the objectives, methods, and potential hazards of participation in the RCR. Patients will be told that they are free to refuse to participate and may withdraw their specimens at any time and for any reason during the storage period. A separate, specific signature will be required to document a patient's agreement to provide optional RCR specimens. Patients who decline to participate will not provide a separate signature.

The investigator should document whether or not the patient has given consent to participate by completing the RCR Research Sample Informed Consent eCRF.

In the event of an RCR participant's death or loss of competence, the participant's specimens and data will continue to be used as part of the RCR research.

#### **4.5.8.6 Withdrawal from the Roche Clinical Repository**

Patients who give consent to provide RCR specimens have the right to withdraw their specimens from the RCR at any time for any reason. If a patient wishes to withdraw consent to the testing of his or her specimens, the investigator must inform the Medical Monitor in writing of the patient's wishes through use of the RCR Subject Withdrawal Form and, if the study is ongoing, must enter the date of withdrawal on the RCR Research Sample Withdrawal of Informed Consent eCRF. The patient will be provided with instructions on how to withdraw consent after the trial is closed. A patient's withdrawal from Study BH29812 does not, by itself, constitute withdrawal of specimens from the RCR. Likewise, a patient's withdrawal from the RCR does not constitute withdrawal from Study BH29812.

#### **4.5.8.7 Monitoring and Oversight**

RCR specimens will be tracked in a manner consistent with Good Clinical Practice (GCP) by a quality-controlled, auditable, and appropriately validated laboratory information management system, to ensure compliance with data confidentiality as well as adherence to authorized use of specimens as specified in this protocol and in the Informed Consent Form. Study monitors and auditors will have direct access to appropriate parts of records relating to patient participation in the RCR for the purposes of verifying the data provided to Roche. The site will permit monitoring, audits, IRB/EC review, and health authority inspections by providing direct access to source data and documents related to the RCR samples.

## **4.6 PATIENT, TREATMENT, STUDY, AND SITE DISCONTINUATION**

### **4.6.1 Patient Discontinuation**

Patients have the right to voluntarily withdraw from the study at any time for any reason. In addition, the investigator has the right to withdraw a patient from the study at any time. Reasons for withdrawal from the study may include but are not limited to the following:

- Patient withdrawal of consent at any time
- Any medical condition that the investigator or Sponsor determines may jeopardize the patient's safety if he or she continues in the study
- Investigator or Sponsor determines it is in the best interest of the patient
- Patient non-compliance, defined as consistent failure to show up for scheduled visits

Every effort should be made to obtain information on patients who withdraw from the study before the withdrawal. The primary reason for withdrawal from the study should be documented on the appropriate eCRF. However, patients will not be followed for any reason after consent has been withdrawn.

If a patient withdraws consent, this request must be documented in the source documents and signed by the investigator. At the time of withdrawal of consent, the patient will be asked if he or she agrees to be followed for survival information. This agreement must be documented and signed by the investigator. Study personnel may use a public information source (e.g., county records) to obtain information about survival status.

### **4.6.2 Study Treatment Discontinuation**

Study treatment (obinutuzumab *or rituximab* and idasanutlin) should be permanently discontinued in patients who experience any of the following:

- DLT during *the DLT window* in patients enrolled in the dose-escalation phase
- Anaphylaxis, acute respiratory distress, or Grade 4 IRR
  - If a Grade 3 IRR is recurrent during the second and subsequent cycles, study treatment may be discontinued at the discretion of the investigator, following an individual benefit• risk assessment.
- Any adverse event that leads to a delay of more than 21 days in the start of the next treatment cycle
- Any hematologic adverse event that meets criteria for permanent discontinuation per guidelines provided in Section 5.1.5
- Grade • 3 non-hematologic adverse event that has a reasonable possibility of being related to study treatment and is either life threatening or does not resolve to Grade <2 within 21 days
- Disease progression
- Pregnancy

The primary reason for study treatment discontinuation should be documented on the appropriate eCRF.

Patients who discontinue study treatment will not be replaced, except as outlined below:

- During the dose-escalation phase (Part 1), patients who discontinue study treatment prior to completing Cycle 1 for reasons other than toxicity will be replaced.
- Patients discontinued before having received at least one dose of each component of the combination will be replaced.

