#### **5.1.1.2 Tumor Lysis Syndrome**

TLS, including fatal events, has been reported with obinutuzumab administration. Patients at risk for TLS (e.g., because of bulky disease or renal insufficiency) should receive adequate hydration and premedication with allopurinol or an alternative uricostatic agent as indicated in Section 4.3.2.6 (see Table 9). Additional guidelines for management of TLS in this study are provided in Section 5.1.5.

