#### **5.1.2.6 Tumor Lysis Syndrome**

Patients treated with rituximab may be at risk for TLS. Severe TLS is very rare in patients receiving rituximab (occurring in < 1 of 10,000 patients), based on postmarketing experience. Signs and symptoms (e.g., hyperuricemia, hyperkalemia, hypocalcemia, hyperphosphatemia, acute renal failure, and elevated LDH) that are consistent with TLS have been reported to occur after the first rituximab IV infusion in patients with high numbers of circulating malignant lymphocytes. A high number of circulating malignant cells ( $\bullet$  25,000/mm^3) or high tumor burden confers a greater risk of TLS. For patients with evidence of TLS, rituximab should be discontinued, and the patient should be treated as clinically indicated.

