**Table 19 Guidelines for Management of Non-Hematologic Toxicities**

Event	Action to Be Taken
General guidance for treatment delays and discontinuation	
 
When a treatment cycle is delayed because of toxicity resulting from any component of the regimen, all study treatment should be held and resumed together to remain synchronized.
 
If study treatment is withheld for > 21 days because of a toxicity that is attributable to study treatment, permanently discontinue study treatment.
 

IRRs and anaphylaxis	
 
Guidelines for the management of IRRs and anaphylaxis are provided in Section 5.1.1.1 and Appendix 9.
 
In case of Grade 4 IRRs or anaphylaxis, study treatment should be permanently discontinued.
 

TLS	
 
Withhold study treatment.a
 
Correct electrolyte abnormalities, monitor renal function and fluid balance, and administer supportive care, including dialysis as indicated.
 
If symptoms have resolved completely, resume obinutuzumab or rituximab and idasanutlin at full dose
 

New-onset neurologic manifestations suggestive of PML	
 
Withhold study treatment.a
 
Consult with a neurologist if PML is suspected (refer to Section 5.1.1.5 for guidance on investigations).
 
If PML is ruled out, resume obinutuzumab or rituximab and idasanutlin at full dose.
 
If PML is confirmed, permanently discontinue study treatment.
 

AST, ALT, or bilirubin increase: Grade • 3 (or • 10 • ULN for patients with liver involvement)	
 
Withhold study treatment.a
 
If improvement to Grade • 1 (or ≤ 5 • ULN (Grade 2) for patients with liver involvement), resume obinutuzumab or rituximab and idasanutlin at full dose for current and subsequent cycles.
 
Permanently discontinue study treatment for life-threatening liver toxicity (including Hy's Law cases).
 

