**Table 19 Guidelines for Management of Non-Hematologic Toxicities (cont.)**

Event		Action to Be Taken
		taking idasanutlin and all expelled tablets are still intact, another dose may be given and the second dose noted in the drug log. Otherwise, no replacement dose is to be given.
Dermatologic toxicity		Permanently discontinue rituximab in the event of Stevens-Johnson syndrome or toxic epidermal necrolysis.
Other non-hematologic toxicities (i.e., not described above), excluding alopecia, nausea, and vomiting	Grade 3 or 4	
For patients who have had no prior dose reductions:
 
 
Withhold study treatment.a
 
If improvement to Grade • 1 or baseline, resume obinutuzumab or rituximab at full dose and resume idasanutlin at a reduced dosea for current and subsequent cycles according to guidelines in Section 5.1.5 for current and subsequent cycles.
 
 
For patients who have had one prior dose reduction:
 
Grade 4 events
 
 
Permanently discontinue study treatment.
 
 
Grade 3 events
 
Withhold study treatment.a
 
 
If improvement to Grade • 1 or baseline, resume obinutuzumab or rituximab at full dose and idasanutlin at a reduced dose according to guidelines in Section 5.1.5 for current and subsequent cycles.
 
 
For patients who have had two prior dose reductions or for patients who reach the lowest dose level and no further dose reduction is applicable (See Section 5.1.1.5):
 
Permanently discontinue study treatment.

	Grade 2	
 
Withhold study treatment.a
 
If improvement to Grade • 1 or baseline, resume obinutuzumab or rituximab at full dose and idasanutlin at current dose
 

h = hour; IRR = infusion-related reaction; PML = progressive multifocal leukoencephalopathy; QD = once a day; TLS = tumor lysis syndrome; ULN = upper limit normal.

a Treatment delays apply to all events; dose modifications apply only to events that are considered to be related to any of the study treatment components. Toxicities that occur during the cycle and subside prior to the next cycle should not trigger the suggested dose modifications.

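### Section 4.6.2 permanently stops study treatment after a related, life-threatening non-hematologic event, but two rows of Table 19 lack that stop and, read literally, restart it; Section 5.1.2.6 and the TLS row also disagree on rituximab

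*Combined protocol and SAP*

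**What the plan says.** **Section 4.6.2 (Study Treatment Discontinuation)** lists events after which the antibody and idasanutlin are permanently stopped. One is a non-hematologic event of Grade 3 or higher, possibly related to treatment, that "is either life threatening or does not resolve to Grade <2 within 21 days". This bullet makes no exception for a first event or for TLS, and it does not refer to Section 5.1.5. The hematologic bullet does: "Any hematologic adverse event that meets criteria for permanent discontinuation per guidelines provided in Section 5.1.5".

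**Table 19 (Section 5.1.5.1, induction), other non-hematologic toxicities, Grade 3 or 4.** The first group is headed "For patients who have had no prior dose reductions". Treatment is withheld, and then "If improvement to Grade • 1 or baseline, resume obinutuzumab" or rituximab at full dose, with idasanutlin at a reduced dose. A Grade 4 stop appears only for patients with one prior reduction. Patients with two prior reductions, or with no further reduction available, also stop. Footnote a adds: "Toxicities that occur during the cycle and subside prior to the next cycle should not trigger the suggested dose modifications".

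**Table 19, TLS row.** Treatment is withheld. "If symptoms have resolved completely, resume obinutuzumab" or rituximab, together with idasanutlin, at full dose. The row has no grade limit.

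**Section 5.1.2.6 (rituximab risks):** "For patients with evidence of TLS, rituximab should be discontinued, and the patient should be treated as clinically indicated".

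**Section 5.1.1.2 (obinutuzumab risks):** "Additional guidelines for management of TLS in this study are provided in Section 5.1.5". Section 5.1.3.4 gives the same direction for idasanutlin.

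**The concern.** For some patients the protocol gives opposite instructions. A patient who has been at immediate risk of death from a related event is taken off treatment by Section 4.6.2. Under a literal reading of Table 19 the same patient receives the drugs again after recovery, at full dose if the event was TLS.

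A DLBCL patient on rituximab with life-threatening TLS faces three texts: stop everything (Section 4.6.2), discontinue rituximab with nothing said about idasanutlin (Section 5.1.2.6), or resume both drugs at full dose (Table 19).

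The stake is patient safety and consistent conduct across about 25 sites. Whichever text a site follows, it departs from another.

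**Working it through.** No arithmetic decides this point. The check sets the rules side by side and looks for a sentence that ranks them.

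**1. Do the rules cover the same patients?** Section 4.6.2 needs three things: a non-hematologic event of Grade 3 or higher, possible relation to treatment, and life threat (or slow resolution). Section 5.2.2 defines life threatening as immediate risk of death in the investigator's view. Table 19 cannot be confined to unrelated events, because footnote a ties dose modifications to related ones. The populations therefore overlap.

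**2. What does each rule tell the site to do?**

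| Case (during induction) | Section 4.6.2 | Table 19 |
|---|---|---|
| Related, life-threatening Grade 4 event in the 'other' row; no prior reduction; recovers to Grade 1 within 21 days | Permanent stop | Resume antibody at full dose and idasanutlin at a reduced dose |
| Related, life-threatening TLS that resolves completely | Permanent stop | Resume antibody and idasanutlin at full dose |

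In the first case, footnote a read literally goes further. If the event subsides before the next cycle, no reduction is triggered and the patient remains in the group with no prior reductions.

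**3. Do other rows carry the stop?** Yes. Table 19 has its own permanent stop for life-threatening liver toxicity, for Grade 4 diarrhea and for Grade 4 infusion reactions or anaphylaxis. Its absence from the two rows above can therefore be read as permission to resume.

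**4. Is there a ranking sentence?** None was found. Sections 4.3.2, 4.3.2.3 (rituximab) and 5.1 send staff to Section 5.1 or 5.1.5 for discontinuation guidance, and Sections 5.1.1.2 and 5.1.3.4 send them to 5.1.5 for TLS. None of these mentions Section 4.6.2.

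**5. How wide is the overlap?**
- Table 21 defines Grade 4, for events not listed in CTCAE, as life-threatening consequences or a need for urgent intervention. Only part of Grade 4 meets Section 4.6.2.
- In dose escalation, Section 3.1.2.1 makes most Grade 3 or 4 non-hematologic events in the window DLTs, and a DLT already stops treatment. The conflict remains after the window and throughout expansion-phase induction.

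**6. The rituximab disagreement is separate.** Section 5.1.2.6 has no severity limit, does not say whether discontinuation is permanent, and does not mention idasanutlin. The TLS row names rituximab as a drug to resume. This mismatch does not depend on the event being life threatening.

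**7. Frequency.** The documents give no rate for related, life-threatening events in either row. For TLS, Section 5.1.2.6 puts severe cases at fewer than 1 in 10,000 patients on rituximab. For 40 DLBCL patients that is below 40 × 1/10,000 = 0.004 expected cases from rituximab alone, with no allowance for idasanutlin. Section 5.1.3.4 says clinical features of TLS were rare with idasanutlin in AML. Section 5.1.1.2 says fatal TLS has been reported with obinutuzumab.

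**The case against.** The strongest reply is that the texts can be applied in sequence. Section 4.6.2 is a stop list triggered by any listed event. Table 19 is headed as guidelines, and its footnote calls its dose changes suggested. Nothing says that recovery lifts a stop already triggered. On this reading both rows keep real content: Grade 3 events, unrelated events, Grade 4 events needing urgent intervention without immediate risk of death, and TLS that is not life threatening or not related. Discontinuing rituximab under Section 5.1.2.6 could also mean a temporary halt.

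This reading is available and sensible. What does not stand is the assumption that a site will reach it. The protocol never states it, its pointers lead to Section 5.1.5, and neighboring rows write their own stops.

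The reply also notes safeguards. Serious events and TLS of any grade are reported within 24 hours, and the investigator may withdraw a patient from the study at any time. These help, but they do not tell a site which rule applies.

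Two stronger readings are tempting and are not supported:

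- **That Table 19 restarts treatment after any first Grade 4 event.** The row is keyed to prior dose reductions. A first Grade 4 event after one reduction, or where no further reduction is possible, is a permanent stop.
- **That the diarrhea and liver rows also contradict Section 4.6.2,** because they allow a restart at Grade 2. That depends on when the 21 days begin, which Section 4.6.2 does not say. If they count delay or withholding, as other 21-day rules in the protocol do, no days have been used at the scheduled next Day 1 and there is no conflict at that visit. Nor can the diarrhea rate be used as an upper limit on the number affected. The 9% of 34 patients in Table 14 is about 3 patients, a point estimate with an exact 95% confidence interval of about 2% to 24%.

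**Conclusion.** The point holds in a limited form. For related, life-threatening non-hematologic events, two induction rows of Table 19 lack the permanent stop that Section 4.6.2 requires and, read literally, restart treatment. The TLS row and Section 5.1.2.6 also disagree on rituximab.

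The conclusion rests on the Section 5.2.2 meaning of life threatening and on the absence of any sentence ranking the texts. It applies mainly after the DLT window or in the expansion phase. Expected frequency is low but cannot be quantified for the combination. The consequence in an affected patient could be serious, so this should be corrected. It is a patient-safety and conduct point: it does not affect the primary analysis, the sample size or the confidence intervals.

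A reader might infer that the protocol intends to re-treat patients after life-threatening events. The documents do not show that; they show an omission that a site could read that way.

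**What to change.** 1. Add to the TLS row, and to the row for other Grade 3 or 4 toxicities with no prior dose reductions: *permanently discontinue study treatment if related and life threatening (Section 4.6.2)*.
2. Make the TLS row and Section 5.1.2.6 agree. State whether rituximab may be resumed after TLS that was not life threatening and, if not, whether idasanutlin continues.

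A general sentence that Section 4.6.2 prevails is not recommended. Section 4.6.2 is not limited to induction, and Table 20 allows study treatment to be withheld for up to 42 days during maintenance. A blanket rule would override that with the 21-day limit.

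The cost is wording in one amendment, with no new data or procedures.
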